- continuously and systematically collect, evaluate, and archive relevant demographic and clinical information on patients belonging to chronic pain treatment centers, making it available for studies and research.
- promote the use of uniform and comparable classification systems, definitions, and records in the structures participating in the database.

- Define the flow of patients referring to pain therapy centers to allow adequate health planning and the priority areas of intervention of the national health plan.

The data collected will facilitate the planning of future studies aimed to:

- define the impact of chronic pain at a local and national level, and its territorial and temporal variations over time, through prevalence and incidence measures;
- identify clinical subtypes, risk factors, predisposing and triggering factors;
- increase knowledge in the field of chronic pain to standardize diagnostic/therapeutic pathways and promote adequate management strategies.

2. Objectives

Primary Outcomes

Identify the profiles of patients belonging to pain therapy centers in terms of:

1. Location and type of pain
2. Prescribed therapies
3. Effectiveness of therapies
4. Time needed to reach the efficacy outcome

Secondary Outcome

1. Evaluate the proportion of patients who reach the outcome of 30 or 50% improvement
2. Evaluate the healthcare resources used in terms of number of visits and time needed to achieve the best outcome (30 or 50% improvement)
3. Identify patient profiles that are related to clinically significant outcomes and the specific treatments performed, plus their intermediate surrogate outcomes in relation to specific patterns

4. Describe the relevant clinical variables in the study population. In particular, the absolute and relative frequencies of those clinical variables relevant to the effectiveness of the treatment will be described, categorized by type of treatment, and the timing of the start of treatment with respect to the onset of pain. The data collected may be used for predictive analyses.

3. Study Design

This is a prospective, multicenter, non-profit observational cohort study. No intervention on patients outside of common clinical practice is envisaged.

The study is divided into three phases.

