Once enrolled, the patient will be followed prospectively until the end of enrollment. At each visit it will be possible to retrieve the patient's chart and fill in the data relating to the intensity of pain and the treatments undertaken. It will also be possible to modify or add an etiological diagnosis in forms of secondary chronic pain. There is no limit to the number of follow-ups for each patient as long as the database is active (3 months from the date of enrollment of the last patient, considering a 12-month active enrollment expected for this study).

Data gathered

The activities of the registry do not replace routine diagnostic tests or visits to your doctor. The data collected by the registry will include relevant demographic data of the patient, comorbidities, the duration of the pain (> 5 years; from 1 to 5 years; from 1 year to 6 months; from 3 to 6 months), the type of pain, the location of the pain, the intensity of the pain (Brief Pain Inventory- Severity (BPI-S) and pain interference in daily activities (Brief Pain Inventory- Interference (BPI-I), treatments received (categorized according to pharmacological therapy, infiltrative therapy, ablative or neuromodulatory therapy, implants), the tests conducted, the number of other medical specialists contacted for the pathology being studied, the professional who sent it to the center. Specifically, the data collected is shown in Attachment 1
In particular, patients will be characterized by:

Type of pain (chronic primary or chronic secondary according to the scheme proposed by IASP)

Location of pain according to the following scheme (multiple options are possible)

- Lower back pain
- Thoracic
- Upper arts
- Lower limbs
- Head/Neck
- Pelvis

Pain Intensity

Brief Pain Inventory-Severity (BPI-S)

Interference with daily activities

Brief Pain Inventory-Interference (BPI-I)

Clinical information related to the pathology

Therapy
Pharmacological
Infiltrative
Implantable

Data collection methods and anonymization

The data collected will be used for scientific and epidemiological purposes. Each data will be created by a participating center and recorded on the SIAARTI Servers via a web application using the RedCap® data management software.

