6. ENDPOINT

Primary Endpoint

The number of patients referring to the centers, the type of pain, the proportion of patients who reach the clinically significant outcome, the type of therapies prescribed (pharmacological, neuromodulatory or implanted) necessary to achieve the outcome and the number of accesses and the Time in which a clinically significant improvement will be achieved (Change in BPI-s or BPI-I; a reduction of > 30% is considered clinically significant and a reduction of > 50% is considered optimal, the data will be evaluated for each Item).

Secondary Endpoint

1. The effectiveness of the treatments will be described in terms of
 - a. Change in pain intensity according to the Brief Pain Inventory-Severity questionnaire (BPI-S) A reduction of > 30% is considered clinically significant and optimal a reduction > of 50% the data will be evaluated for each Item)
 - b. b. Change in pain interference on daily activities according to the Brief Pain Inventory-Interference questionnaire (BPI-I). A reduction of > 30% is considered clinically significant and a reduction of > 50% is considered optimal; the data will be evaluated for each item)
2. Proportion of patients achieving clinically significant outcomes in relation to baseline characteristics and specific treatments performed and their intermediate surrogate outcomes in relation to specific patterns.
3. Resources used: Number of visits to the center for each patient in a year; Number of ordinary or day hospitalizations for each patient in a year.
4. The clinical variables relevant to the outcome will be described (e.g. type of pain, comorbidities, the time between treatment and clinically significant improvement, type of therapy undertaken - pharmacological, invasive, implant-based)

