12. ETHICAL CONSIDERATIONS

This observational study is designed and will be conducted according to the current protocol, in accordance with EU Directive 2001/20/EC relating to the implementation of the principles of good clinical practice in the conduct of clinical trials on medicinal products for human use, in accordance with the principles published in Good Clinical Practice (GCP) guidelines and in accordance with the Declaration of Helsinki on Ethical Principles for Medical Research Involving Human Subjects, adopted by the General Assembly of the World Medical Association (1996),

The investigator guarantees that personal patient data will be protected and processed in accordance with the General Data Protection Regulation (EU) 2016/679 (GDPR) on data protection and privacy.

ATTACHMENT 1

DATA GATHERED FOR EACH PATIENT

- ◇ CENTER CODE
- ◇ UNIQUE PATIENT CODE
- ◇ ACCESS METHOD (TO BE COMPLETED ONLY THE FIRST TIME FOR EACH PATIENT)
- ◇ DATE (the CRF must be filled in each time the patient has a visit/admission)
- ◇ SENT BY:
 - FAMILY DOCTOR
 - OTHER SPECIALIST
 - ADVICE FROM A RELATIVE/ACQUAINTANCE
 - WEB SEARCH
- ◇ REFERRAL METHOD (TO BE COMPLETED ONLY THE FIRST TIME FOR EACH PATIENT)
 - ◇ FIRST ANESTHESIOLOGICAL VISIT
 - ◇ ANESTHESIOLOGICAL CHECK-UP EXAMINATION
 - UNDER CARE AT THE CENTER FOR:
 - > 5 years;
 - from 1 to 5 years;
 - from 1 year to 6 months; or 3 to 6 months;
 - < 3 months
 - ◇ ORDINARY HOSPITALIZATION
 - IN EMPLOYMENT AT THE CENTER FOR:
 - > 5 years;
 - from 1 to 5 years;
 - from 1 year to 6 months; or 3 to 6 months;
 - < 3 months
 - ◇ DAY HOSPITALITY (DAY SURGERY OR DAY HOSPITAL)
 - IN EMPLOYMENT AT THE CENTER FOR:
 - > 5 years;
 - da 1 a 5 anni;
 - da 1 anno a 6 mesi; o da 3 a 6 mesi;
 - < 3 mesi

LEVEL 1: DEMOGRAPHICS

- ◇ AGE
- ◇ SEX
 - M
 - F

STATE/COUNTY OF RESIDENCE

SCHOOL LEVEL

- ◇ Not Known
- ◇ Grade School
- ◇ High School
- ◇ University

WORK

- ◇ WORKER
- ◇ UNEMPLOYED

COMORBIDITIES

- ◇ CARDIOVASCULAR
- ◇ DIABETES
- ◇ RESPIRATORY
- ◇ AUTOIMMUNITY
- ◇ CHRONIC INFLAMMATION
- ◇ OTHER

LEVEL 2: DIAGNOSIS

TYPE OF PAIN

- ◇ PRIMARY CHRONIC
 - CHRONIC WIDESPREAD PAIN
 - FIBROMYALGIA
 - OTHER
 - CRPS

- HEADACHE OR OROFACIAL PAIN
- MUSCULOSKELATAL
 - LOW-BACK PAIN
 - ALTRO
- ◇ SECONDARY CHRONIC
 - ONCOLOGICAL
 - POSTSURGICAL
 - LUMBAR
 - CERVICAL
 - BREAST
 - INGUINAL HERNIA
 - THORACOTOMY
 - OTHER
 - POST TRAUMATIC
 - CRPS
 - OTHER
 - NEUROPATHIC
 - PERIFERAL
 - POST-TRAUMATIC
 - DIABETIC
 - TRIGEMINAL
 - POST-HERPETIC

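### The primary endpoint's therapy types omit infiltrative therapy, which the form collects as its own class, and the pain-location list cannot record abdominal or other unlisted sites

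*Protocol*

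**What the plan says.** Section 2 of the protocol opens its primary outcomes with "Location and type of pain" and "Prescribed therapies". The classes for the second of these are then stated in several places:

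- Section 5, Data gathered, running text: treatments are "categorized according to pharmacological therapy, infiltrative therapy, ablative or neuromodulatory therapy, implants". Attachment 1, Level 3, has the same four blocks.
- Section 5, short Therapy list at the end of Data gathered: pharmacological, infiltrative, implantable.
- Section 6, Primary Endpoint: "the type of therapies prescribed (pharmacological, neuromodulatory or implanted) necessary to achieve the outcome".
- Section 6, Secondary Endpoint 4: "pharmacological, invasive, implant-based", in a parenthesis introduced as examples.

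For location, Section 5 gives "Location of pain according to the following scheme (multiple options are possible", followed by lower back, thoracic, upper limbs (misprinted), lower limbs, head/neck and pelvis. Attachment 1, Area of pain, has the same six entries. The type-of-pain list in Attachment 1 includes "CHRONIC WIDESPREAD PAIN" and visceral pain.

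**The concern.** An endpoint that reports therapy by type needs one type for each therapy the form records. A patient who improves after an epidural or facet-joint infiltration has no named type in the primary endpoint. One analyst might leave that therapy out of the table, and another might count it as neuromodulatory. Both would be following the protocol, and their tables by type would not be the same.

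The location list raises a different question. A category list for a primary descriptive outcome should cover every patient who can be enrolled. Sections 4 and 5 admit patients whatever the cause of their pain, and Section 4 wants the criteria kept broad so as to reflect national practice. If a site is not on the list, the distribution of locations is wrong for those patients and no stored data can put it right.

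**Working it through.** No formula applies, and the protocol gives no figure to reproduce. The check sets the lists side by side.

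**Therapy classes**

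| Place | Pharmacological | Infiltrative | Neuromodulatory/ablative | Implants |
|---|---|---|---|---|
| Section 5, running text | yes | yes | yes | yes |
| Attachment 1, Level 3 | yes | yes | yes | yes |
| Section 5, short list | yes | yes | **no** | yes |
| Section 6, primary endpoint | yes | **no** | yes | yes |
| Section 6, secondary endpoint 4 (examples) | yes | not named; *invasive* | not named; *invasive* | yes |

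The short list and the primary endpoint each drop a class that the other keeps, so neither abbreviates the other. Neither is marked as illustrative.

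Top-level procedure entries in Attachment 1:

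- infiltrative: 5 (epidural, intra-articular, facet joints, sacro-iliac, peripheral nerve);
- neuromodulatory/neuroablative: 5;
- implants: 5 (two spinal cord stimulator types, peripheral nerve stimulation, ganglionic stimulation, intrathecal pump);
- total: 5 + 5 + 5 = 15.

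So 5 of 15 entries have no named class in the primary endpoint, and a different 5 of 15 have none in the short Section 5 list. These are counts of form entries, not of patients. All 15 are recorded individually, so any grouping can be rebuilt later once the intended one is stated.

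**Location**

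| Site | Section 5 list | Attachment 1 list | Other route on the form |
|---|---|---|---|
| Abdomen | no | no | none for the site; visceral is a type of pain, not a place |
| Any other unlisted site | no | no | none |
| Widespread | no | no | several regions can be ticked; also a diagnosis |
| Groin after hernia surgery | not named | not named | pelvis or lower limbs is plausible; also a diagnosis |

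Only the first two rows have no route. The absence of *other* is not a general rule of the form: comorbidities, several diagnosis sub-lists, instrumental exams and drugs all have it.

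The two problems differ in kind. Therapy is recorded in full and described inconsistently. Location is described consistently and recorded incompletely.

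**The case against.** The best defence is that Attachment 1 governs what is collected, and it holds all four therapy classes item by item. Grouping items for tables is ordinary analysis-plan work, and Section 8 leaves detailed plans to later protocols. This stands as far as therapy data are concerned: nothing is lost. It does not reconcile the primary endpoint with the form, because the endpoint itself names the types and leaves one out.

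A reader might infer that the protocol has four mutually contradictory therapy schemes. That goes too far. Secondary endpoint 4 offers its list as examples, and a coarser grouping in another endpoint is not a contradiction. The conflict that stands is between the primary endpoint, the short Section 5 list and the four-class scheme.

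A reader might also infer that widespread pain and pain after hernia surgery cannot be located. The documents do not support this. Regions are multi-select, widespread pain is a diagnosis of its own, and groin pain has plausible regions. Thoracic or pelvic visceral pain also has a region.

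Finally, Phase 1 is a three-month pilot meant to settle the dataset and how data are entered. That is a fair point about timing: it gives the correction a natural place. It does not show that the correction will be made, since the location list is already fixed in both Section 5 and Attachment 1.

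**Conclusion.** The point holds in two parts of unequal weight.

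1. **Therapy classes: a conflict of wording.** The primary endpoint names no class for infiltrative therapy (5 of 15 procedure entries), and the short Section 5 list names none for neuromodulatory/ablative therapy (another 5 of 15). The item-level data survive, so this can be repaired at any time.
2. **Location: a gap in data capture.** Abdominal pain and any other site outside the six regions cannot be recorded correctly for the first primary outcome, and analysis cannot repair this.

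The share of patients affected is not given and cannot be derived from the protocol. The location part assumes only that some enrolled patients have pain at an unlisted site, which open enrolment by cause and a visceral category make likely. No sample size or error rate is involved.

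A reader might go on to infer that the procedure lists are defective because they lack *other*. The protocol does not promise exhaustive capture of procedures and no missing procedure has been identified, so that would be a preference and not an error.

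**What to change.** - In Section 6, state the therapy types of the primary endpoint as the four Attachment 1 classes: pharmacological, infiltrative, neuromodulatory/neuroablative, implants.
- Complete the short Therapy list in Section 5 in the same way and, for consistency, use the same classes in secondary endpoint 4.
- Add *abdomen* and *other (specify)* to the location list in both Section 5 and Attachment 1, and make the change in REDCap during the Phase 1 pilot, before the full registry opens. Records entered before the change will lack the options.
- Do not add a *widespread* location. Ticking several regions and the existing diagnosis already cover it, and a third route would let the same patient be coded in different ways.

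The cost is a few lines of protocol text, two form options and some coding of free-text sites.

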Phase 1, expected to last three months, involves the participation of 7 centers proposing the project and aims to structure the dataset and data entry methods. Actions will also be implemented for dissemination of the project by trying to recruit centers distributed across the national territory. Estimated start date 01/03/2023.

In phase 2, the project expands to the centers that wish to join, and this protocol will be fully operational.

The duration of phase 2 is two years and six months, presumably starting from 01/06/2023. Patient enrollment at each center will begin at different times depending on the rollout of the registry and local ethics committee approval. It is likely that the first patient will be prospectively enrolled in 01/06/2023. The last patient will be enrolled by 01/03/2025 and it will be possible to enter data and follow-up until 01/09/2025. The results of this study will be available by 01/12/2025.

Once the patient has been enrolled, it will be possible to trace the patient's personal file and update it at each follow-up until the end of enrollment.

In phase 3, SIAARTI will promote the register at the institutions for the establishment of a national register compliant with the DECREE OF THE PRESIDENT OF THE COUNCIL OF MINISTERS 3 March 2017 "Identification of surveillance systems and registers of mortality, tumors and other pathologies. (17A03142) (GU General Series n.109 of 12-05-2017)"

Setting

The study aims to collect demographic and clinical data from patients belonging to pain therapy centers recognized at the regional level and belonging to the pain therapy networks established in compliance with law 38/2010 and according to the Agreement between the Government and the Regions of 25 July 2012.

Patients will be registered regardless of the access modality (outpatient or hospitalization) and will be characterized by pathology and treatments performed. The participation of centers for the treatment of pediatric pain is expected. Data relating to patients under the age of 18 will be analyzed separately.

The database aims to follow the patients enrolled according to a code that makes them anonymous.

Participating Centers

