8. STATISTICAL ANALYSIS

All enrolled patients registered in the registry will be included in the analyses. A descriptive analysis will be performed on the collected data. In general, qualitative variables will be described using frequency distributions; the quantitative variables will be described by mean and standard deviation if normally distributed, and by median and interquartile range if asymmetrically distributed. As appropriate, statistical tests will be used for exploratory purposes. Treatment effects (Change in BPI-S and BPI-I scores) will be calculated as the ratio of the difference between baseline and follow-up scores to the baseline score. If the data allow it, inferential analysis will be applied on quantitative data (such as: comparison of Student's t means, Fisher's F, etc.), or on qualitative data (such as: chi square, odds ratio, Mann Whitney U, etc.). The prevalence of the different pathologies and the related confidence intervals will be estimated. Detailed statistical analysis plans will be set up in future research protocols that will use this database as a source of data.

Sample Size

Since this is an observational registry, no prior sample size calculation is required. Considering an expected participation of 12 centers, an estimate of 2500 patients included appears reasonable.

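### The primary responder proportion has no assessment time and no deciding score under unequal follow-up, and the time to improvement, summarised as Section 8 states, covers only patients who improved

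*Protocol*

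**What the plan says.** - **Response.** Section 6 (Primary Endpoint) lists "the proportion of patients who reach the clinically significant outcome" and states no time at which it is assessed.
- **Time.** The same sentence lists "the Time in which a clinically significant improvement will be achieved (Change in BPI-s or BPI-I", with the thresholds "a reduction of > 30% is considered clinically significant and a reduction of > 50% is considered optimal", and adds that "the data will be evaluated for each Item". Attachment 1 has four BPI-S pain items and seven BPI-I items. No rule says which scale or item decides response.
- **Change.** Section 8 defines it relative to the baseline score but does not say which follow-up visit is used.
- **Visits.** Section 5 (Follow-up procedure): "There is no limit to the number of follow-ups for each patient as long as the database is active". No schedule is fixed.
- **Calendar.** Section 3: "The last patient will be enrolled by 01/03/2025 and it will be possible to enter data and follow-up until 01/09/2025". The first enrolment is expected on 01/06/2023. Section 3 also says that files are updated until enrolment ends. Section 5 repeats this, and then has the database active until 3 months after the last enrolment, with 12 months of enrolment.
- **Summaries.** Section 8 includes all enrolled patients, uses frequency distributions for qualitative variables, and says that "the quantitative variables will be described by mean and standard deviation if normally distributed, and by median and interquartile range if asymmetrically distributed". It names no method for patients who have not yet improved.

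**The concern.** A proportion that reaches an outcome can be interpreted only with a time attached. Without one, the natural tabulation counts every patient who has crossed the threshold by the time data entry closes. Early enrollees then have more time to cross than late ones, and frequent attenders have more occasions to be seen crossing. The resulting figure mixes the effect of care with length of observation.

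The time endpoint has a related fault. A patient still unimproved at closure has no time to improvement, so a mean or median can be taken only over those who improved. Slow improvers are more likely to be cut off by closure, so those left in the summary are the faster ones. This also sits badly with the commitment to analyse all enrolled patients.

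Both quantities are primary. Section 2 also wants patient profiles related to clinically significant outcomes, and unequal follow-up would blur those associations.

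**Working it through.** The protocol gives no response rate, so there is no figure of its own to reproduce. The check is date arithmetic followed by an illustration with assumed rates.

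**Step 1. Follow-up windows**

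| Statement | Longest | Shortest |
|---|---|---|
| Section 3 closing date: 01/06/2023 or 01/03/2025 to 01/09/2025 | 27 months | 6 months |
| Sections 3 and 5, until enrolment ends: 01/06/2023 to 01/03/2025 | 21 months | 0 months |
| Section 5: 12 months of enrolment plus 3 months | 15 months | 3 months |

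The three windows disagree and must be reconciled. Follow-up is unequal under each of them.

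**Step 2. Probability of counting as a responder**

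Assume a constant improvement rate λ per month. The probability of having improved by month t is 1 − exp(−λt). With λ = 0.06:

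- 6 months: 1 − exp(−0.36) = 0.302
- 27 months: 1 − exp(−1.62) = 0.802
- 3 and 15 months: 1 − exp(−0.18) = 0.165 and 1 − exp(−0.90) = 0.593
- 0 and 21 months: 0 and 1 − exp(−1.26) = 0.716

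Patients with an identical outlook therefore differ by 43 to 72 percentage points between the ends of a window.

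**Step 3. Time to improvement among improvers**

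Take follow-up as uniform on 6 to 27 months (an assumption) and λ = 0.06.

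- True median: ln 2 / 0.06 = 11.6 months.
- Share ever seen to improve: 1 − [exp(−0.36) − exp(−1.62)] / (0.06 × 21) = 1 − (0.698 − 0.198)/1.26 = 0.603.
- Half of that share is 0.302. Everyone is followed for at least 6 months, so 1 − exp(−0.06t) = 0.302 gives t = 6.0 months as the improvers-only median.

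Simulation gives the same 6.0 months. At other rates the improvers-only median against the true median is 7.1 against 23.1 months (3% per month) and 4.9 against 6.9 months (10% per month).

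**Step 4. The other windows**

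Simulated with a true median of 12 months (λ = ln 2 / 12 = 0.058) and uniform follow-up:

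| Window | Ever improved | Improvers-only median |
|---|---|---|
| 6 to 27 months | 59% | 6.1 months |
| 3 to 15 months | 39% | 3.8 months |
| 0 to 21 months | 42% | 4.6 months |

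The improvers-only median is well below 12 months in every window. The headline proportion moves by 20 points with the calendar alone.

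**Step 5. What a fixed time gives**

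With λ = 0.06, the proportion improved is 16% at 3 months, 30% at 6 months and 1 − exp(−0.72) = 51% at 12 months, whatever the enrolment date.

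**The case against.** Several points against the concern have force.

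- **Descriptive registry, and perhaps a separate analysis plan.** Section 8 offers its mean-or-median rule as a general one and does not tie it to time to improvement. A censored-data method could sit in a plan that is not shown. That limits the criticism to the summaries as stated. It does not reach the missing time and score, which define the primary endpoint and belong in the protocol. The protocol can set a horizon: secondary endpoint 3 counts visits and admissions per year.
- **Either-score reading.** A reader might infer that response on BPI-S or BPI-I, or on any single item, suffices. The text does not say so. It calls for evaluation item by item, and secondary endpoints 1a and 1b treat the scales separately. What stands is that no deciding score is named, so no inflation from a composite can be charged to the plan.
- **Centre comparison.** A reader might infer that late-opening centres will be ranked unfairly. No objective or endpoint compares centres, and territorial variation is left to future studies.
- **Cut-off wording.** Section 6 uses strict inequalities, while Section 2 says "Evaluate the proportion of patients who reach the outcome of 30 or 50% improvement". The latter is shorthand in an objective and Section 6 supplies the definition, so this is a minor inconsistency.
- **Limits of a censored estimate.** Kaplan-Meier estimates of first improvement still count chance crossings at repeated visits. In a simulation with no true change (assumed mean 6.5, SD 2, reliability 0.7), a BPI-S fall above 30% appeared in 9% of patients with one visit and 30% with six. Censoring may also be informative if patients stop attending because they are better or dissatisfied. Both points stand and should be stated as limitations.

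**Conclusion.** The concern holds in this form: the primary responder proportion lacks an assessment time and a deciding score while follow-up differs by enrolment date. As stated, the Section 8 summaries give a proportion that depends on length of follow-up and a time to improvement that is too short.

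At an assumed constant 6% per month, the contrast is 30% against 80% responders at 6 and 27 months, and a median of 6.0 against 11.6 months. These sizes rest on the assumed rate, uniform follow-up and the Section 3 closing dates. Only the direction is firm, and it is the same in all three windows. A reader might take 6 to 27 months as settled by Section 3, but that section also says that files are updated until enrolment ends.

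The registry remains usable. The endpoint definition and the summaries should be changed before the results are analysed.

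**What to change.** In Sections 6 and 8:

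1. Name one score as the responder outcome, for example the BPI-S mean, with BPI-I and single items as supportive.
2. Report the proportion improved and the time to first improvement as Kaplan-Meier estimates at fixed times, for example 3, 6 and 12 months. Count from the BPI at enrolment and censor at the last visit with a BPI.
3. Show newly referred patients separately from those already in care at enrolment. Section 5 admits both, and Attachment 1 allows for more than 5 years under care.
4. State as limitations that improvement is seen only at need-driven visits, that censoring may be informative, and that these estimates do not remove chance crossings from repeated visits.
5. Reconcile the follow-up statements in Sections 3 and 5, and use one wording of the 30% and 50% cut-offs in Sections 2 and 6 (minor).

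The cost is wording and slightly more analysis. Attachment 1 already asks for a dated form at each visit or admission, so no new data are needed. The downside is a headline proportion that may look less favourable than a count of patients who ever improved.

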 - OTHER
 - CENTRAL
 - POST-ISCHEMIC
 - SM
 - TRIGEMINAL
 - NEURODEGENERATIVE DISEASES
 - HEADACHE OR OROFACIAL PAIN
 - VISCERAL
 - SKELETAL MUSCLE
 - LOW-BACK-PAIN
 - OTHER

AREA OF PAIN

- ◇ LOWER BACK PAIN

- ◇ THORACIC
- ◇ UPPER LIMBS
- ◇ LOWER LIMBS
- ◇ HEAD/NECK
- ◇ PELVIS

PAIN INTENSITY AND INTERFERENCE

- ◇ BPI-S

WORST PAIN IN THE LAST 24 HOURS

• 1 • 2 • 3 • 4 • 5 • 6 • 7 • 8 • 9 • 10

LEAST PAIN IN THE LAST 24 HOURS

• 1 • 2 • 3 • 4 • 5 • 6 • 7 • 8 • 9 • 10

AVERAGE PAIN IN THE LAST 24 HOURS

• 1 • 2 • 3 • 4 • 5 • 6 • 7 • 8 • 9 • 10

CURRENT PAIN

• 1 • 2 • 3 • 4 • 5 • 6 • 7 • 8 • 9 • 10

HOW MUCH RELIEF HAVE YOU HAD FROM THE THERAPY (%)

• 10 • 20 • 30 • 40 • 50 • 60 • 70 • 80 • 90 • 100

BPI-I (PAIN INTERFERENCE ON)

ACTIVITY IN GENERAL

• 0 • 1 • 2 • 3 • 4 • 5 • 6 • 7 • 8 • 9 • 10

MOOD

• 1 • 2 • 3 • 4 • 5 • 6 • 7 • 8 • 9 • 10

ABILITY TO WALK

• 1 • 2 • 3 • 4 • 5 • 6 • 7 • 8 • 9 • 10

NORMAL WORKING ABILITY (both at home and outside)

• 1 • 2 • 3 • 4 • 5 • 6 • 7 • 8 • 9 • 10

RELATIONSHIPS WITH OTHER PEOPLE

• 1 • 2 • 3 • 4 • 5 • 6 • 7 • 8 • 9 • 10

SLEEP

• 1 • 2 • 3 • 4 • 5 • 6 • 7 • 8 • 9 • 10

PLEASURE OF LIVING

• 1 • 2 • 3 • 4 • 5 • 6 • 7 • 8 • 9 • 10 • 1 • 2 • 3 • 4 • 5 • 6 • 7 • 8 • 9 • 10

REQUESTED EXAMS

- ◇ INSTRUMENTAL EXAMS
 - XRAY
 - MRI
 - SCINTIGRAPHY
 - EMG/ENG
 - OTHER
- ◇ LABORATORY EXAMS

COMPLETED EXAMS

- CLINICAL EXAMINATION OF SENSITIVITY
- QST-TEST
- DIAGNOSTIC BLOCK

LEVEL 3: THERAPY

PHARMACOLOGICAL THERAPY

- ◇ SNRI
- ◇ GABAPENTINOIDS
- ◇ TRICICLICS
- ◇ OPIOIDS
 - TRAMADOL
 - CODEINE/PARACETAMOL
 - OXYCODONE/PARACETAMOL
 - MORPHINE SR
 - MORPHINE IR
 - OXYCODONE
 - OXYCODONE/NALOXONE
 - HYDROMORPHONE
 - TAPENTADOL
 - TRANSDERMAL FENTANYL
 - TRANSMUCOSAL FENTANYL
 - BUPRENORPHINE
 - METHADONE

- ◇ NSAIDs
 - AS NEEDED
 - INTERVALS/REGULARLY (indicate how many days)
- ◇ COXIB
 - AS NEEDED
 - INTERVALS/REGULARLY (indicate how many days)
- ◇ PARACETAMOL
- ◇ OTHER

INFILTRATIVE THERAPY

- ◇ EPIDURAL
- ◇ INTRA-ARTICULAR (SHOULDER, KNEE, ANKLE, HIP, ECC)
- ◇ SPINAL FACET JOINTS
- ◇ SACRO-ILIAC
- ◇ PERIPHERAL NERVE

NEUROMODULATORY/NEUROABLATIVE THERAPY

- ◇ GANGLIAR RADIOFREQUENCY
- ◇ RADIOFREQUENCY OF PERIPHERAL NERVES
- ◇ CRIOAMODULATION
- ◇ EPIDUROLYSIS
- ◇ EPIDUROSCOPY

IMPLANTS

- ◇ SCS NON-RECHARGABLE
 - CERVICAL
 - DORSAL
- ◇ SCS RECHARGABLE
 - CERVICAL
 - DORSAL
- ◇ STIMULATION OF PERIPHERAL NERVE
- ◇ GANGLIAR STIMULATION
- ◇ INTRATHECAL PUMP

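### Section 2 speaks of reaching a 30 or 50% improvement, but Section 6 counts only reductions strictly above those figures, so an exact halving on a whole-number BPI item misses the 50% tier

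*Protocol*

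**What the plan says.** Section 2 (Objectives) names the outcome twice by its figure. Secondary Outcome 1 is "Evaluate the proportion of patients who reach the outcome of 30 or 50% improvement". Secondary Outcome 2 covers visits and "time needed to achieve the best outcome (30 or 50% improvement". Neither gives an operator.

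Section 6 (Endpoint) does. The primary endpoint states that "a reduction of > 30% is considered clinically significant and a reduction of > 50% is considered optimal". Secondary Endpoint 1a, for BPI severity, repeats the strict sign: "A reduction of > 30% is considered clinically significant and optimal a reduction > of 50" per cent. Secondary Endpoint 1b, for BPI interference, does the same. Section 6 also sets the unit of evaluation: "the data will be evaluated for each Item".

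Section 8 (Statistical Analysis) defines change as "calculated as the ratio of the difference between baseline and follow-up scores to the baseline score". Attachment 1 records every item, such as "WORST PAIN IN THE LAST 24 HOURS", as a whole number. Most items are printed 1 to 10; general activity is printed 0 to 10.

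**The concern.** A patient whose score falls from 8 to 4 has, in ordinary usage, reached a 50% improvement. Section 2 would count that patient and Section 6 would not. On a continuous score the choice between > and ≥ would make no practical difference. Here it does, because the protocol evaluates single whole-number items and divides by the baseline, so exact halvings are ordinary observations.

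The boundary decides who enters the 50% proportion (Secondary Outcome 1) and when the 50% outcome is reached (Secondary Outcome 2). With the strict sign the proportion is lower, and the time and number of visits are the same or greater, than if reaching 50% counted. Two analysts could each cite the protocol and report different figures for the same data.

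**Working it through.** **Inputs.** Thresholds of 30% and 50% with a strict sign (Section 6); change = (baseline − follow-up) / baseline (Section 8); whole-number item scores (Attachment 1). The protocol states no figure of its own for this point, so there is none to reproduce.

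**Step 1: the 50% tier.** With baseline b and fall d, the rules are d/b > 0.5 and d/b ≥ 0.5. They differ only where d = b/2 is a whole number, that is, for even b. Smallest qualifying fall:

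| Baseline | Strict > 50% | At least 50% |
|---|---|---|
| 10 | 6 points (60%) | 5 points (50%) |
| 9 | 5 (55.6%) | 5 (55.6%) |
| 8 | 5 (62.5%) | 4 (50%) |
| 7 | 4 (57.1%) | 4 (57.1%) |
| 6 | 4 (66.7%) | 3 (50%) |
| 5 | 3 (60%) | 3 (60%) |
| 4 | 3 (75%) | 2 (50%) |
| 3 | 2 (66.7%) | 2 (66.7%) |
| 2 | not reachable on an item printed 1–10 | 1 (50%) |

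The changes that switch class are 10→5, 8→4, 6→3, 4→2 and 2→1. Of the 55 possible non-worsening score pairs on a 1–10 item, 20 are optimal under > and 25 under ≥. These are counts of possible pairs, not expected patient proportions.

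**Step 2: the 30% tier.** A tie needs d = 0.3b to be a whole number. For b from 1 to 10 this happens only at b = 10, with d = 3, so only 10→7 switches: 4 points (40%) are needed under > against 3 (30%) under ≥. The qualifying pairs go from 33 to 34 of 55. An exact halving still passes the 30% tier under either sign.

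**Step 3: possible size.** The gap between the two proportions is the share of patients with an exact tie on that item. The protocol gives no distribution, so every figure here is an assumption. Rounded, correlated item scores were simulated:

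- 360 settings, item baseline above 4 (baseline mean 6–7.5, SD 1.5–2; follow-up mean 3.5–5.5, SD 1.5–2.5; correlation 0.2–0.6): gap at 50% of 1.8–16.8 percentage points, median 8.1; gap at 30% of 0.06–5.2, median 1.0.
- 648 settings on a wider grid, no baseline restriction (baseline mean 3–8, mean fall 0.5–3): gap at 50% of 0.3–16 points if follow-up scores can go to 0, and 0.3–25 if they stop at 1.

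The fair summary for the 50% tier is therefore under 1 to about 25 points per item.

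**The case against.** The strongest reply is that Section 2 sets no boundary at all. It gives a short label without an operator, and Section 6 supplies the working rule, written the same way three times. The primary endpoint in Section 6 itself speaks of patients reaching the clinically significant outcome in the sentence that defines it with >, so the verb alone does not prove that an exact tie should count. An analyst who follows Section 6 has one rule to apply. This stands in part: Section 2 may well be shorthand, and a reader who infers a flat contradiction goes further than the text allows. What remains is that Section 6 attaches the verb to a named category, while Section 2 attaches it to the figure, and nothing says how an exact 30% or 50% is to be classed under Section 2.

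A second reply is that a ≥ sign may have been lost in translation or in reading the file. That cannot be excluded, but > appears in all three statements. If the source carries ≥, correcting the sign is all that is needed.

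A third is that falls of 60 to 75% follow from whole-number scoring and are no error in themselves. That is right: odd baselines need 55.6 to 66.7% under either rule. The point concerns only the even baselines, where the choice of sign adds a further point to the fall required.

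**Conclusion.** The point stands as a minor boundary mismatch between Sections 2 and 6. The arithmetic on ties follows from the protocol alone: every even baseline is affected at 50%, and only baseline 10 at 30%.

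A reader might infer that the primary endpoint is materially distorted. The documents do not support that. Its proportion and time rest on the 30% tier, where only 10→7 changes class. A reader might also want one firm figure for the effect on the 50% proportion. None can be given; the range above depends wholly on assumed means, spreads, correlations and the lowest score allowed. The study is a descriptive registry without a sample size calculation, so no power or error rate depends on the sign. What depends on it is the reported 50% proportion and the time and visits to that outcome.

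**What to change.** Write ≥ 30% and ≥ 50% in the three places in Section 6 (primary endpoint, Secondary Endpoints 1a and 1b), so that the rule counts patients who reach the improvement that Section 2 names. This needs no new data, because the ratio in Section 8 is already calculated. The only downside is that the reported 50% proportion rises by the share of patients with an exact halving on that item; the 30% proportion hardly moves.

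If the sponsor intends the strict rule, report the proportion as more than 50% and give beside it the number with a reduction of exactly 50%, so that readers can obtain either figure.
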